6.10.5 Definition of Serious Adverse Events

A serious adverse event (SAE) is any untoward medical occurrence that at any dose:

- Results in death
- Is life-threatening at the time of the event
- Requires inpatient hospitalisation
- Results in persistent or significant disability or incapacity
- Is another important medical event

6.10.6 Reporting of Serious Adverse Events

If an SAE occurs, trial personnel must fill in a “Serious Adverse Event reporting form” and notify the Investigator immediately. The Investigator should report all SAEs (whether or not considered related to trial treatment) to the Sponsor within 24 h after awareness of the SAE. The reporting by the Investigator to the Sponsor should cover the seriousness criteria, intensity and initial causality assessment.

The initial report of a SAE should as far as possible be supplemented by detailed information on diagnosis/symptoms, the relationship with the start of treatment and the latest dose of trial treatment taken and any further relevant data. A follow-up report of the SAE will be written as applicable and sent to the Sponsor.

6.10.7 Follow-up of Adverse Events and Serious Adverse Events

After an AE or SAE, the subject should be followed by any clinical or biological examination, considered as necessary by the medical judgment of the Investigator, until the AE/SAE has resolved, stabilised, the Investigator deems further observations or examinations to be no longer medically indicated or until the subject is under professional medical care. Follow-up should always be performed until a potential causality between the trial treatment and the AE has been assessed.

7.1 Trial Files

The following documents will be present at the clinical site before trial start can take place:

- Signed confidentiality and clinical trial agreement between the site and sponsor
- IEC approval of the protocol and informed consent document
- Signed protocol page
- Blank copy of the IEC-approved informed consent document and any other documents to the subjects
- Blank copy of the CRF
- Laboratory manual
- Signed Investigator / site agreement
- Insurance certificate from Sponsor
- CVs of Investigator and sub-investigators
- Site signature and responsibility log

Copies of these documents as well as supplemental information, such as the Investigational Product Information and final protocol should be kept on-site in a dedicated investigator's trial file, which should be kept strictly confidential. This file should also contain subject accountability records (screening and randomisation logs), investigational product accountability records (receipt/dispensing), Sponsor/Investigator correspondence, IEC correspondence, protocol deviations, biological samples records, and SAE/Safety reports. The Investigator will keep a list of the subjects, identifying the names (with addresses and/or medical dossier numbers), their respective code number and the dates of start and end of the trial, in order to verify the concordance between the data contained in the CRFs and that in the source documents (European Directive 91/507/EEC).

All source documentation (i.e. medical notes etc.) should be available in print at the site.

7.2 Retention of Records

No trial documents will be destroyed or moved to a new location without prior written approval from the Sponsor. If the Investigator relocates, retires, or withdraws from the clinical trial for any reason, all records required to be maintained for the trial should be transferred to an agreed-upon designee, such as another Investigator at the institution where the trial was conducted.

7.3 Publication of Results

After completion of the trial, the results will be tabulated, evaluated and issued as a complete final clinical trial report. A summary of the report will be sent to the IEC, if applicable according to the local regulations.

All data generated by this clinical trial is the sole property of the Sponsor who will use the information for communications, regulatory purposes and/or publications as appropriate according to the clinical development plan for the trial product. All information from the trial is strictly confidential and should not be published or disclosed in any form without prior written agreement of the Sponsor.

The sponsor aims to make the data from the trial publicly available via scientific papers in appropriate scientific journals. The Principle Investigator and sub investigators will be included in scientific publications based on the trial. Authorship to other trial personnel can only be given to persons who fulfil the “Uniform Requirements for Manuscripts Submitted to Biomedical Journals” from the International Committee of Medical Journal Editors. Persons, who do not meet these criteria will be acknowledged in a publication, if they wish to.

8 Trial Administrative Structure

**List of Abbreviations**

AE	Adverse Event
AOM	Acute Otitis Media
AUC	Areas under the curve
BMI	Body mass index
CFU	Colony Forming Units
CI	Confidence Interval
CRA	Clinical Research Associate
CRO	Contract Research Organization
CV	Coefficient of Variation
eCRF	Electronic Case Report Form
EFSA	European Food Safety Authority
ePRO	Electronic Patient Reported Outcome
FAO	Food and Agricultural Organization
FAS	Full- analysis set
FDA	US Food and Drug Administration
GCP	Good Clinical Practice
GDPR	General Data Protection Regulation
GI	Gastrointestinal
GP	General Practitioner
GRAS	Generally Regarded as Safe
Guardian	Parent or Legal Guardian
HR	Hearth rate
ICH	International Conference on Harmonisation
IEC	Independent Ethics Committee
IRB	Institutional Review Board
Mg	Milligram
LRTI	Lower Respiratory Tract Infections
Min	Minutes
mL	Milliliter
N	Sample Size
PI	Principle Investigator
PP	Per protocol
QC	Quality Control

Chr. Hansen A/S  
Trial Id: HND-GI-036  
Author: AH  
Statistical Analysis Plan

Date:  
Version No.:  
Status:  
Page:

4. February 2021  
v1.0  
FINAL  
6 of 15

*Confidential*

**Signifikans**

QPS	Qualified Presumption of Safety
QQ	Quantiles-Quantiles
RA	Regulatory Authority
RTI	Respiratory Tract Infections
SAE	Serious Adverse Event
SAP	Statistical Analysis Plan
SAS	Safety Analysis Set
SD	Standard Deviation
URTI	Upper Respiratory Tract Infections
WHO	World Health Organization

Chr. Hansen A/S  
Trial Id: HND-GI-036  
Author: AH  
Statistical Analysis Plan

Date: 4. February 2021  
Version No.: v1.0  
Status: FINAL  
Page: 7 of 15

*Confidential*

**Signifikans**

## 1 Introduction and Summary

### 1.1 Introduction

The present Statistical Analysis Plan (SAP) describes in detail and in accordance with ICH-GCP guidelines (1) and Signifikans Aps SOPs the statistical analyses to be carried out for the HND-GI-036 trial.

### 1.2 Summary

The table below provide an overview of all analyses performed on the primary, secondary and exploratory endpoints.

### Primary and Secondary Outcome Variables

Variables	Time point	Endpoint	Analysis performed
Primary outcome variables	Week 2, 3 4 and 5	Lanza score	Generalized Estimating Equations (GEE) model including the following terms: Treatment (Bif195 or Placebo), Sequence (First Bif195 or Placebo), Period (1 and 2) and baseline (visit 2) value
Secondary outcome variables (safety and efficacy)	Week 2, 3 4 and 5	Blood safety parameters: Creatinin, Potassium, Sodium, ALAT, ASAT, HbA1c, Glucose (from HbA1c), CRP, Leucocytes, Thrombocytes Blood efficacy parameters: Erytrocytes, Haematocrit, Haemoglobin, INR	Each parameter will be analysed using a proc mixed model with patient as Random effect. The following terms will be including in the model: Treatment (Bif195 or Placebo), Sequence (First Bif195 or Placebo), Period (1 and 2) and baseline (visit 2) value

## 2 Trial Objective

### 2.1 Primary Objectives

Clinical evaluation of stomach and duodenum via the (5-scale) Lanza score.

**0 = no visible lesions**

**1 = redness and hyperemia in mucosa**

**2 = 1 or 2 erosions or hemorrhaging lesions**

**3 = 3-10 erosions of hemorrhaging lesions**

**4 = >10 erosions or hemorrhaging lesions or an ulcer**

Erosions = mucosal disruption denuded of villi with or w/o exudates or red color

Ulcer = large erosion with central area with exudates

Ref: Soylu et al. 2008, World J Gastroenterol, 14(43), 6704-6710

### 2.2 Secondary Objectives

Safety blood parameters:

Blood safety parameters: Creatinin, Potassium, Sodium, ALAT, ASAT, HbA1c, Glucose (from HbA1c), CRP, Leucocytes, Thrombocytes

[figure not shown]
Efficacy blood parameters:

Erytrocites, Haematocrit, Haemoglobin, INR

### 3 Trial Design

#### Study design (HND-GI-036)

- Aspirin 300 mg/day (1 capsule at breakfast)
- Placebo or 100 B CFU Bif195/day (1 capsule at breakfast, 1 capsule in the evening)

## 4 Trial Population

For the statistical analysis, the randomized subjects will be divided into the following datasets:

Full Analysis Set (FAS):	Subjects who are randomized and have consumed at least one dose of study product and for whom efficacy data is available.
No response to challenge (NC)	Subjects not responding on the Aspirin challenge response defined as having Lanza score=0 on all visits (visits 2, 3 4 and 5)
Modified FAS (mFAS)	FAS population minus NC population.
Per Protocol Set (PPS)	Subjects, who are randomized and have consumed at least one dose of study product, have available efficacy data and have no major protocol deviations

All endpoints will be analyzed on the FAS populations. For sensitivity analysis, selected analyses will also be performed on the mFAS and PPS.

## 5 Statistical Methodology

### 5.1 General statistical considerations

All statistical tests will be assessed using a nominal two-sided significance level of 5%.

The two treatment groups will be labelled as Bif195 and Placebo.

Weeks will be calculated as number of days divided by 7

Months will be calculated as number of days divided by 30.4375

Years will be calculated as number of days divided by 365.25

Number of days will be calculated using end date minus start date +1.

### 5.2 Subject disposition

An overall summary table of the subject disposition will be prepared with number of patients in the following categories (and sub-categories):

- Screened and randomized patients
- Analysis populations (FAS and mFAS)
- End of study reason

### 5.3 Handling of Missing Data and Dropouts

No imputation of data will be carried out in case of missing data, but all available data will be used.

### 5.4 Primary Efficacy Outcome Variable

Primary efficacy variable: Lanza score ranging from 0 (no visible lesions) to 4.

Change from baseline prior each period will be calculated and used in the analysis i.e. (visit 3 minus visit 2) (visit 5 minus visit 4).

This ordinal endpoint will be analysed using a Generalized Estimating Equations (GEE) model including the following terms:

- Treatment (Bif195 or Placebo)
- Sequence (first Bif195 or Placebo)
- Period (1 and 2)
- Baseline (visit 2) value

The model will take in to account the crossover design of the study with same patients having a result after both treatments.

- 1) Firstly, the analyse will include terms of Treatment, Sequence, period and baseline (visit 2) value
- 2) If no significant terms of either sequence or period, the factors will be removed from the model prior evaluating treatment effect

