We aim for 20 subjects to complete the trial, and assuming a drop-out rate around 20%, we aim to randomise 25 subjects. Subjects that drop out or are withdrawn from the study can be replaced. We expect for up to 50 subjects to be screened for participation.

Main Criteria for Inclusion

- Written informed consent
- Healthy and without any gastrointestinal discomfort/pain or other significant symptoms
- Age ≥ 18 and ≤ 40 years
- Willing to abstain from any other probiotic products and/or medication known to alter gastrointestinal function throughout the participation of the trial

ASA challenge product

The ASA product used during the ASA challenge periods will be the 300 mg Aspirin oral tablet from Alliance Pharmaceuticals, Ireland. Subjects will consume 300 mg ASA daily together with the trial product/placebo and breakfast.

Test Product

The investigational product is a vegetable capsule containing *Bifidobacterium breve* DSM 32356. Subjects will consume 1 capsule together with ASA and breakfast and 1 capsule in the evening, equivalent to a dose of minimum $100*10^9$ CFU daily. All product will be produced at the trial sponsor Chr. Hansen laboratories in Hørsholm, Denmark, which are certified for food production.

Reference Product (placebo)

The reference product (placebo) is the same vegetable capsule, identical in composition, taste and appearance, but without bacteria. Subjects will consume 1 capsule daily with ASA and breakfast and 1 capsule in the evening. Placebo capsules will be produced at Chr. Hansen laboratory in Hørsholm, Denmark, which is certified for food production.

Duration of ASA challenge: **Two times 4 weeks**

Duration of trial product/placebo intervention: **Two times 4 weeks**

Criteria for Evaluation

Endpoints, all exploratory:

- The effects of daily intake of Bif195 versus placebo on transcriptomics measured in ventricle and upper small intestinal mucosal biopsies obtained before and after a 4-week ASA challenge
- The effects of daily intake of Bif195 versus placebo on microbiota composition profile measured in ventricle and upper small intestinal mucosal biopsies obtained before and after a 4-week ASA challenge
- The effects of daily intake of Bif195 versus placebo on proteomics profile measured in ventricle and upper small intestinal mucosal biopsies obtained before and after a 4-week ASA challenge

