6.2 Trial Design

This trial is a single-site, randomised, double-blinded, placebo-controlled, two-armed, cross-over trial in 25 healthy volunteers.

The trial will investigate effects of daily intake of the *Bifidobacterium breve* Bif195 or placebo when co-administered with daily intake of 300 mg of ASA.

The trial includes a run-in period of two weeks duration followed by a 4-week intervention period where Bif195/placebo and ASA are co-administered. This period is followed by a 6-week wash-out period before a new 4-week period is performed with Bif195/placebo and

ASA co-administration. Bif195 and placebo interventions are performed double-blinded in randomised order for each subject in a cross-over design.

Subjects will participate in the trial for a total duration of approximately 17 weeks including the run-in phase. Besides the screening visit, the trial will consist of 4 visits at site and 4 phone visits.

After having given their written informed consent, subjects will complete the screening procedures to evaluate their eligibility for participation in the trial and complete a run-in period of two weeks duration to washout possible pre-trial probiotics and/or use of medication. Four days after baseline assessments at Visit 2, all subjects will start daily intake of 300 mg ASA and Bif195 or placebo in a ratio of 1:1 according to the randomisation performed at Visit 2.

At visit 2 – 5, all subjects will be biopsied from the upper small intestine and the ventricle during a gastroscopy procedure. At each of these 4 visits, 6 biopsies will be taken from pre-specified locations in the duodenum and 2 biopsies will be taken from the ventricle (approximately 5 mg each). Luminal fluids will also be collected during the gastroscopy (approximately 2 mL per visit) and one blood sample (of maximum 25mL per visit) will be collected. During the entire trial subjects will be instructed to maintain their habitual life style with regards to diet, physical activity level and sleep habits.

The analysis on biopsies will include a combination of transcriptomics analysis, microbiome analysis, proteomics profiling and metabolomics profiling. In addition, a clinical evaluation of the damage to the ventricle and the duodenum will be provided via the Lanza score. Also, a general safety monitoring, blood sampling and subject baseline phenotype will be obtained.

[figure not shown]

Figure 1 Visit overview

Table 1 Trial flow chart

Visit	1	2		3		Wash-out	4		5	

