6.9.8 Statistics and power calculation

Data will be entered into a database and analysed using statistical software. The effect of the intervention on the endpoints will be assessed using paired statistical analysis and the level of significance will be set to 0.05. Pathway analysis will also be performed using a more explorative approach.

Previous studies using the same endoscopy procedure with biopsies being analysed for arrays of gene expression have showed an approximate negative binomial distribution and a coefficient of variation of 0.344. Assuming a negative binomial distribution of the data in the present study, we have calculated that a sample size of 20 will result in a power of 0.95 for identifying genes that are down or up-regulated more than 1.5-fold as a consequence of Bif195 intervention at a significance level of 0.05. In order to achieve this statistical power, we aim to have 20 subjects completing the intervention. Assuming a drop-out rate of around 20%, we aim to randomise 25 subjects.

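### SAP 5.4 names no link, test or small-sample correction for the primary Lanza GEE in 20–25 subjects; run as an ordinary linear GEE, its nominal 5% test would have a true size of about 7–8%

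*SAP*

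**What the plan says.** SAP 5.4 sets the outcome: "Primary efficacy variable: Lanza score ranging from 0 (no visible lesions) to 4". The analysed quantity is a difference of two grades: "Change from baseline prior each period will be calculated and used in the analysis", that is visit 3 minus visit 2 and visit 5 minus visit 4. The method follows: "This ordinal endpoint will be analysed using a Generalized Estimating Equations (GEE) model including the following terms". A second step then applies: "If no significant terms of either sequence or period, the factors will be removed from the model prior evaluating treatment effect".

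SAP 5.1 sets the error level (the figure is a percentage): "All statistical tests will be assessed using a nominal two-sided significance level of 5". SAP 5.3 imputes nothing and uses all available data. SAP section 4 sends selected analyses to the mFAS and PPS as sensitivity analyses.

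On numbers, protocol 6.9.8 says "we aim to have 20 subjects completing the intervention", and the synopsis gives the same target: "We aim for 20 subjects to complete the trial, and assuming a drop-out rate around 20%, we aim to randomise 25 subjects".

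The SAP does not state the link, working correlation, variance estimator, Wald or score test, reference distribution, any small-sample correction, or what to do if the primary model does not converge. SAP 5.5 does give the blood parameters a non-parametric fallback.

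**The concern.** Standard GEE inference takes its standard error from the scatter of cluster-level residuals and refers the result to a normal distribution. Both steps are large-sample approximations. Here a cluster is a subject, and there are only 20 to 25. The sandwich makes no allowance for the parameters fitted, and the normal reference ignores the uncertainty in the variance. Both errors push the p-value down and narrow the interval.

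At stake is whether the one test the SAP calls primary holds the 5% level set in SAP 5.1. A second risk is that a cumulative-logit fit breaks down on sparse change categories (possible values −4 to +4), which would leave the analyst to improvise after seeing the data.

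**Working it through.** **Inputs.** Two-sided 5% (SAP 5.1); 20 completers and 25 randomised (protocol synopsis and 6.9.8); two periods with one change score each, and a model with treatment, sequence, period and visit 2 baseline (SAP 5.4). The documents give no Lanza distribution.

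**The plan's own figure.** The only operating characteristic calculated in the documents is power of 0.95 for a 1.5-fold change in gene expression with CV 0.344 and 20 subjects. It reproduces approximately: SE = √(2×0.344²/20) = 0.109; ln 1.5 / 0.109 = 3.73; Φ(3.73 − 1.96) = 0.96. Drop-out: 20/(1 − 0.2) = 25. Neither figure bears on the Lanza test, for which the plan gives only the nominal 5%.

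**Linear GEE, full model, complete pairs.** Sequence and visit 2 baseline are constant within a subject, so they cancel from the within-subject treatment contrast. What remains is a comparison of mean period differences between the two sequences, with n − 2 degrees of freedom. The uncorrected sandwich divides the sum of squares by n instead of n − 2, and the Wald test uses 1.96. Hence

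- true size = P(|t(n−2)| > 1.96·√((n−2)/n))
- width relative to the correct interval = 1.96·√((n−2)/n) / t(0.975, n−2)

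n=20: cut-off 1.96·√(18/20) = 1.859; size **7.9%**; width 1.859/2.101 = 0.885, so 11.5% too narrow.

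n=25: cut-off 1.96·√(23/25) = 1.880; size **7.3%**; width 1.880/2.069 = 0.909, so 9.1% too narrow.

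**Linear GEE with sequence and period both dropped.** The contrast is then the mean within-subject difference, with n − 1 degrees of freedom.

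n=20: cut-off 1.96·√(19/20) = 1.910; size **7.1%**; width 1.910/2.093 = 0.913, so 8.7% too narrow.

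n=25: cut-off 1.96·√(24/25) = 1.920; size **6.7%**; width 1.920/2.064 = 0.930, so 7.0% too narrow.

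**Simulation under no effect** (0–4 scores from assumed latent distributions; mainly 5,000 or 12,000 runs per scenario for the linear model, 1,500 or 4,000 for the cumulative logit):

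| Analysis | Rejection rate |
|---|---|
| Linear, sandwich, Wald z, full model | 7.0–8.5% |
| Same, after the sequence/period step | 6.6–8.1% |
| Linear, robust score test, full model | 5.0–5.4% |
| Linear, robust score test, both terms dropped | 4.4–4.8% |
| Mancl–DeRouen SE with t(n−2), full model | 3.1–4.8% |
| Mancl–DeRouen SE with t(n−2), after the step | 3.8–5.3% |
| Two-period crossover t-test | 4.0–5.8% |
| Cumulative logit, sandwich, Wald | about 5–7.5% |

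The cumulative-logit result varies with the assumed lesion distribution. One set of runs gave 4.6–5.8% with no failed fits. Another gave 5.3–6.2% with 0–7.5% failing. A third gave 4.8–7.6% among converged fits, with 0.2–20% failing. In one extreme scenario with almost no lesions, where the challenge has in effect failed, size was about 10% and 11% of fits failed.

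**Smaller sets.** The documents give no mFAS or PPS size. With n=12, assumed purely for illustration, the full linear model gives a cut-off of 1.96·√(10/12) = 1.789 and a size of 10.4%.

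**The case against.** A reader might infer that the SAP commits the primary test to uncorrected large-sample standard errors, so that it is anti-conservative however it is run. The documents do not support that. SAP 5.4 says only GEE and SAP section 6 names only SAS; the sandwich with a Wald z test is usual practice, not something the plan writes down. SAP 5.4 calls the endpoint ordinal, while SAP 5.5 reserves the mixed model and normality checks for interval-scale blood data. That contrast favours a cumulative logit, whose size is nearer nominal. A robust score test, equally open under the text, is close to 5% even for the linear model.

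It can also be said that the full-model figures overstate the interval most likely to be reported: in null simulations, sequence and period were both dropped in about 84–85% of runs. The excess is then roughly 2 percentage points. Protocol 6.7 lists both Lanza endpoints as exploratory.

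All of this stands, and it limits the point. It does not remove it. The modelled variable is a numeric change, SAP 5.8 lays out a numeric result with no link, and an analyst who follows the text faithfully could run the version that misses 5%. Dropping sequence and period reduces the excess but does not remove it. The cumulative-logit route is not reliably nominal either, and it has no fallback.

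**Conclusion.** The concern holds in a conditional form. Under a linear GEE with an uncorrected sandwich and Wald z test, size is 7.9% (n=20) or 7.3% (n=25) in the full model, and 7.1% or 6.7% once sequence and period are both removed. These analytic figures assume complete pairs and near-normal period differences; the simulations on discrete scores agree with them. Under a cumulative logit, size depends on a lesion distribution that nobody can state in advance, and the fit may fail. The cumulative-logit figures rest wholly on assumed distributions.

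This goes beyond missing detail, because one ordinary way of carrying out the plan does not hold its own 5% level and better methods are readily available. Severity is minor to moderate: the excess is 2 to 3 points, it applies under one reading, and the endpoint is exploratory in the protocol though primary in the SAP.

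**What to change.** In SAP 5.4, state the link, working correlation, variance estimator and test, and use small-sample inference for the primary p-value and interval.

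- **If linear:** use a bias-corrected sandwich (for example Mancl–DeRouen) with a t reference on n − 2 degrees of freedom. This also accommodates subjects with only one period, which matters given SAP 5.3 and the expected drop-out. With complete pairs and no covariate, the two-period crossover t-test is the corresponding simple choice.
- **If cumulative logit:** take the p-value from a test that re-randomises the sequence labels. For non-convergence, pre-specify the statistic as the between-sequence difference in the mean period difference of the change score.
- **mFAS and PPS:** apply the same rules.

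The cost is one SAP paragraph, a few lines of code and slightly larger p-values. Intervals become about 8–13% wider with the crossover t-test (1/0.930 = 1.075 to 1/0.885 = 1.130), which is their correct width. Mancl–DeRouen with t is somewhat more conservative. In the full model with complete pairs it widens the uncorrected interval by a factor of (20/18)×(2.101/1.960) = 1.19 at n=20 and (25/23)×(2.069/1.960) = 1.15 at n=25, consistent with its simulated size of 3.1–4.8%.

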### 5.5 Secondary Safety Outcome Variables

Secondary safety outcome variables: Blood safety parameters: Creatinin, Potassium, Sodium, ALAT, ASAT, HbA1c, Glucose (from HbA1c), CRP, Leucocytes, Thrombocytes

Each parameter will be analysed using a proc mixed model with patient as Random effect.

Sequence and period effect will be evaluated prior evaluating the treatment effect in a similar way as the primary efficacy outcome variable.

For statistical analysis of data measured on an interval scale model check is assessed using QQ residual plots together with Kolmogorov-Smirnov test for normality.

In case for normality not reached using untransformed data nor transformed data using the log2-scale, appropriate non-parametric statistical methods will be used instead.

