### 5.6 Secondary Efficacy Outcome Variables

Secondary Efficacy outcome variables: Erythrocytes, Haematocrit, Haemoglobin, INR. All variables are analysed like the secondary safety outcome variable analysis.

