## 5.9 Challenge analysis

The challenge model will be analysed comparing baseline (visit 2 and 4) with “after” results (visit 3 and visit 5) using similar model as the primary and secondary outcome analysis with the following terms in the model:

- Treatment (Bif195 or Placebo)
- Sequence (first Bif195 or Placebo)
- Period (1 and 2)
- Before\_after (baseline and “after”)

The challenge model will thereby be analysed adjusted for period, sequence and treatment.

The data will be structured as seen below:

subject	sequence	period	tmt	Before_after	result
1 AB		1 A		before	1
1 AB		1 A		after	2
1 AB		2 B		before	1
1 AB		2 B		after	0
2 AB		1 B		before	4
2 AB		1 B		after	5
2 AB		2 A		before	4
2 AB		2 A		after	5
3 AB		1 B		before	4
3 AB		1 B		after	3
3 AB		2 A		before	4
3 AB		2 A		after	3
4 AB		1 B		before	0
4 AB		1 B		after	3
4 AB		2 A		before	0
4 AB		2 A		after	3
5 AB		1 A		before	4
5 AB		1 A		after	1
5 AB		2 B		before	4
5 AB		2 B		after	1
6 BA		1 A		before	3
6 BA		1 A		after	4
6 BA		2 B		before	3
6 BA		2 B		after	4
7 BA		1 B		before	3
7 BA		1 B		after	2
7 BA		2 A		before	3
7 BA		2 A		after	2

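### SAP 5.4 lets a 5% pre-test remove period from the crossover model; with a real period effect and unequal sequences this biases the treatment estimate, modestly

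*SAP*

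**What the plan says.** For the Lanza score, SAP 5.4 takes the within-period change (visit 3 minus 2, visit 5 minus 4): "Change from baseline prior each period will be calculated and used in the analysis". The model is given as: "This ordinal endpoint will be analysed using a Generalized Estimating Equations (GEE) model including the following terms", followed by treatment, sequence, period and the visit 2 baseline. Step 2 then reads: "If no significant terms of either sequence or period, the factors will be removed from the model prior evaluating treatment effect". No separate level is set for this pre-test, so the general two-sided 5% of SAP 5.1 applies.

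SAP 5.5 extends the rule to the blood safety parameters: "Sequence and period effect will be evaluated prior evaluating the treatment effect in a similar way as the primary efficacy outcome variable". SAP 5.6 does so for the blood efficacy parameters: "All variables are analysed like the secondary safety outcome variable analysis". Parameters that fail the normality check both raw and on the log2 scale go to unspecified non-parametric methods, where this step need not apply.

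The challenge analysis in SAP 5.9 has no removal step: "The challenge model will thereby be analysed adjusted for period, sequence and treatment".

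On missing data, SAP 5.3 says: "No imputation of data will be carried out in case of missing data, but all available data will be used". Subjects with one period therefore stay in.

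**The concern.** Period is a design factor of a two-period crossover. Step 2 lets a significance test in about 20 subjects decide whether it stays in the model that judges treatment. Such a test often misses a moderate period effect. If period is then dropped and the two sequences differ in size, part of the period effect is read as an effect of Bif195.

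The protocol does not assure equal sequences. Section 6.5.5 leaves the block length open and allows for none. Section 6.9.8 expects about 20% dropout. The Synopsis allows replacement, without stating that a replacement takes the same sequence.

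The rule also makes the model depend on chance. With no period or sequence effect at all, 1 − 0.95² = 9.75% of fits keep at least one term. There are 10 safety and 4 efficacy blood parameters. If all 14 went through the mixed model, 14 × 0.0975 ≈ 1.4 of them would be expected to end with a different model from the rest.

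**Working it through.** **Inputs from the documents.** 20 completers, 25 randomised, dropout about 20% (Protocol 6.9.8); 1:1 allocation (Protocol 6.2); 5% two-sided (SAP 5.1). The plan's own figure reproduces: 20/(1 − 0.20) = 25. Its power of 0.95 concerns gene expression and does not bear on this model. The documents give no period effect and no Lanza score distribution, so both are assumed below.

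**Shift from dropping period.** Let d be Bif195 minus placebo within a subject, with mean m1 in the n1 subjects who take Bif195 first and m2 in the other n2. Let π be period 2 minus period 1.

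- Period kept: treatment estimate = (m1 + m2)/2.
- Period dropped: treatment estimate = (n1·m1 + n2·m2)/(n1 + n2).
- Period estimate = (m2 − m1)/2.
- Dropped minus kept = −[(n1 − n2)/(n1 + n2)] × period estimate.

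This is exact for complete pairs, an identity link and a baseline that is constant within subject. The factor is 0 at 10:10, 2/20 = 0.10 at 11:9, 4/20 = 0.20 at 12:8, 6/20 = 0.30 at 13:7 and 8/20 = 0.40 at 14:6. Sequence is orthogonal to treatment and period with complete pairs, so dropping it moves the estimate by 0 at every split.

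Outside those conditions the factor is approximate:

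- With a cumulative-logit link, the ratio to the period log-odds ratio was 0.00 at 10:10, 0.20 at 12:8 and 0.28 at 13:7.
- With 13:12 randomised, 5 lost before period 2 and all data kept, an independence GEE gives 0.08–0.12 (12:8 completers) and 0.17 (13:7). A mixed model gives 0.10–0.18 and 0.20–0.27 for intraclass correlations of 0.2–0.8.

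**Power of the pre-test at 10:10.** With SD_d the SD of the within-subject difference, the standard error of the period estimate is (SD_d/2)·√(1/10 + 1/10) = 0.224 SD_d. Effects of 0.3 and 0.5 SD_d give noncentralities of 1.34 and 2.24 on 18 df, and power of 25% and 56%. In residual within-subject SDs (SD_d = √2 residual SDs), 0.3 and 0.5 give 15% and 32%.

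**The whole two-step rule.** Normal data, complete pairs, no treatment effect, π = 0.5 SD_d, 200,000 runs:

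| Split | Period dropped | Size of mean bias (SD_d) | Type I error, two-step | Type I error, terms kept |
|---|---|---|---|---|
| 10:10 | 44% | 0.000 | 4.8% | 5.0% |
| 11:9 | 45% | 0.014 | 5.0% | 5.0% |
| 12:8 | 46% | 0.029 | 5.5% | 5.0% |
| 13:7 | 48% | 0.044 | 6.6% | 5.0% |
| 14:6 | 51% | 0.065 | 8.5% | 5.0% |

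The largest biases are about 0.13 treatment standard errors at 12:8, 0.19 at 13:7 and 0.27 at 14:6. For a period effect of 0.5 residual SD (0.5/√2 = 0.35 SD_d), the level is about 5.5% at 12:8 and 6.5% at 13:7.

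**Joint removal instead of term by term.** For normal complete pairs the sequence test rests on subject totals, which are independent of the within-subject differences. With no sequence effect, the level is 0.95 × two-step + 0.05 × kept. At 12:8 this is 0.95 × 5.54 + 0.05 × 4.96 = 5.5%. At 13:7 it is 0.95 × 6.60 + 0.05 × 4.97 = 6.5%. The reading barely matters.

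**Lanza change scores.** A latent-normal model cut to 0–4 was simulated, with correlation 0.5 and an assumed ASA shift of 1.0. The analysis used t-tests on the change scores, without the baseline covariate.

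- A latent period shift of 0.6 on visit 5 only gives a mean bias of 0.05–0.06 points at 12:8 and 0.08–0.09 at 13:7, against a treatment standard error of about 0.4. The level is 5.7–5.8% and 6.6–6.7%.
- The same shift on visits 4 and 5 largely cancels. Bias is at most 0.02 and 0.03, and the level 5.4–5.5% and 5.5–5.6%.

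**How likely the splits are.** Five random dropouts from 13:12 (hypergeometric) leave 10:10 with probability 0.36, 11:9 with 0.48, and 12:8 or worse with 0.16; 13:7 is the worst possible (0.015). With 20 subjects and no blocking (binomial), 12:8 or worse has probability 0.50, 13:7 or worse 0.26, and 14:6 or worse 2 × 60,460/2²⁰ = 0.12. Averaged over splits, the level is 5.1–5.3% by the dropout route and 5.3–6.0% without blocking, against 4.9–5.1% with terms kept.

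**The case against.** The strongest reply is that little is at stake. Protocol 6.7 calls every endpoint exploratory. Protocol 6.6.1 has one blinded gastroenterologist score every visit, and the change score removes most drift shared by visits 4 and 5. By the dropout route, 0.36 + 0.48 = 84% of trials end at 10:10 or 11:9. The larger Lanza biases need an assumed shift at visit 5 that is absent at visit 4, a pattern the documents neither state nor exclude. Protocol 6.9.8 also announces a paired analysis without mentioning a period term, which is close to the reduced model. All of this stands and limits the weight. It does not give a reason for the pre-test, and the SAP offers none.

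A reader might infer that the blood parameters are fully exposed to period drift, because SAP 1.2 specifies "Period (1 and 2) and baseline (visit 2) value". The documents do not settle this. SAP 5.7 plans a sensitivity analysis indexed to visits 2 and 4, and the data layout in SAP 5.8, meant for both primary and secondary analyses, has a baseline that changes with period. How much drift cancels depends on which baseline is used; with a period-specific one, the shift formula is approximate.

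A reader might also infer that all 14 blood parameters follow the rule. The non-parametric fallback in SAP 5.5 means that some may not.

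Finally, keeping the terms does not by itself guarantee a 5% level for the GEE. The SAP names neither link nor variance estimator. Had it prescribed an uncorrected Wald z-test, which it does not, the level at 20 subjects would be about 7.9% with terms kept and 7.1% with them dropped (identity link, normal data). That is a separate gap, and this point does not rest on it.

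**Conclusion.** The point holds under both readings of step 2. Bias arises only when there is a true period effect and the sequences are unequal. It rests on assumed period effects and splits, and mostly on normal-theory stand-ins for the ordinal GEE.

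Two stronger conclusions are not supported. One is that the rule makes the primary result invalid: there is no bias at 10:10, and for the period effects tried the level averaged over splits does not exceed about 6.0%. Only an extreme split such as 14:6 brings it near 8.5%. The other is that removing sequence is itself harmful. With complete pairs it changes nothing. With single-period subjects kept, an independence GEE moves by about 0.11–0.13 times any real difference between the sequence groups, but randomisation makes that difference zero on average unless there is carryover. Carryover would bias the within-subject estimate with or without the sequence term.

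The rule still buys under 1 point of power at best, and it gives the treatment comparison less protection than SAP 5.9 gives the challenge analysis. It should be changed as a low-cost improvement of modest weight.

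**What to change.** Delete step 2 of SAP 5.4 and the matching sentence in 5.5, and state: *Treatment, period and sequence stay in every primary and secondary model whatever their p-values.*

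Reconcile the baseline definition: visit 2 only in SAP 1.2 and 5.4, against period-specific in 5.7 and 5.8. Say also that the period-adjusted within-subject comparison is the paired analysis meant in Protocol 6.9.8. As a secondary matter for the Lanza GEE, name the link and variance estimator, and use a test that is valid with 20–25 subjects.

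The cost is SAP wording and 1–2 degrees of freedom. In the simulations, keeping the terms lost 0.7–0.9 points of power at 10:10 with no period effect, and gained 0.3–0.6 points with the 0.6 shift on visit 5.
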